Pediatric experience: Fanale et al (2011) conducted a retrospective analysis of two phase 1 and two phase 2, multicenter brentuximab vedotin drug development studies which included the enrollment of pediatric patients age 12-17 years old. Nine patients (median age=16 years, male=5) were included in this analysis. Patients received brentuximab vedotin, as a 30 minute outpatient infusion, at dose of either 0.8 mg/kg or 1.2 mg/kg weekly for 3 out of 4 weeks or doses of 1.2 mg/kg or 1.8 mg/kg every 3 weeks (median of 15 cycles). The majority (n=6) of patients received 1.8 mg/kg every 3 weeks. Complete response was observed in 6/9 pediatric patients who had treatment-refractory lymphoma. Grade ≥ 3 treatment-emergent adverse events included neutropenia (n=3), white blood cell count decreased (n=1), thrombocytopenia (n=1), catheter site infection (n=1) and hyperesthesia (n=1). No patient discontinued treatment due to an adverse event.

1.4 Rationale for New Cohort :

With 30 evaluable patients to date, data from the phase II portion of this study show an ORR of 75% and a CR rate of 33.3%. Among patients who achieved CR after 2 cycles of treatment, all remained in CR after 2 additional cycles of treatment and were able to proceed to AHCT without further intervening therapy. For patients who only achieved PR or SD after 2 cycles of therapy, 2 additional cycles of brentuximab vedotin, given at the 1.8mg/kg dose, did not change the response rate in any patient, either from PR to CR or SD to PR. Ultimately all patients, with the exception of one went on to AHCT after additional therapy. Although it is medically acceptable and allowed as part of the COH standard operating procedure to take a patient with PR to AHCT, retrospective data from Memorial Sloan Kettering show better PFS when patients enter AHCT with CR as disease status (Moskowitz et al.). For that reason, the majority of our patients in PR or SD received combination chemotherapy such as ICE (ifosfamide, Cyclophosphamide, Etoposide) to convert from PR to CR or SD to PR/CR before AHCT.

Because data from the phase II portion of this study showed that the observed conversion

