7.5 Safety Measurements

Safety measurements will consist of monitoring and recording all adverse events, including serious adverse events, the regular monitoring of hematology, serum chemistry, routine monitoring of vital signs (heart rate, blood pressure, and body temperature) and physical condition. Toxicity will be assessed using the NIH-NCI Common Terminology Criteria for Adverse Events, Version 4.0.

8 STATISTICAL PROCEDURES.

8.1 Sample size calculations.

The aim of this study is to estimate the efficacy of this salvage brentuximab vedotin treatment for Hodgkin lymphoma prior to autologous hematopoietic stem cell transplantation. Treatment will be given once every three weeks in a 21 day cycle. Based on historical data, the assumed ORR in this patient population is 60%. The objective of this study is to be able to detect an ORR of at least 60%. The study will utilize a Simon two-stage optimal design. Twenty three (23) subjects will be enrolled in the first stage. If 12 or more subjects respond, an additional 14 subjects will be enrolled (for a total sample size of 37). The null hypothesis will be rejected if 23 or more of the total sample size of 37 respond. This design is based on the use of a two sided test at the 5% level of significance and provides 80% power.

Analysis: Response rates will be calculated as the percent of evaluable patients that have confirmed CR or PR by radiographic response including CT and/or PET scans, and exact 95% confidence intervals will be calculated for this estimate. Time to response, duration of response, and survival will be estimated using the product-limit method of Kaplan and Meier. Toxicity information recorded will include the type, severity, and the probable association with the study regimen. Tables will be constructed to summarize the observed incidence by severity and type of toxicity. Baseline information (e.g. the extent of prior therapy) and demographic information will be presented, as well, to describe the patients treated in this study.

Based on the current referral patterns it is expected that 37 patients will be enrolled in this study over the course of 3 years.

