In accordance with the primary study objectives, we will perform descriptive statistical analyses on these data after the study is complete. With adequate follow-up time, the endpoints of PFS, overall survival (OS) will be assessed by Kaplan-Meier survival analysis and 95% confidence intervals will be calculated using Greenwood's formula. PFS will be defined as the time from first treatment day (post AHCT) until objective or symptomatic relapse or death as a result of lymphoma or acute toxicity of treatment. OS will be defined as the time from first treatment day (post AHCT) until death. The cumulative incidence of relapse/progression and non-relapse mortality will be calculated as competing risks.

8.2 New Cohort to Test Increased Dosing for Patients Not Achieving CR after Two Cycles

Based on previously published brentuximab vedotin response/toxicity data and data from the phase II portion of this study (see protocol section 1.3), we now propose to accrue up to 20 additional patients in a new cohort that will enroll until we have 10 patients who do not attain CR after two cycles of therapy, and are treated at the increased dose of 2.4 mg/kg of brentuximab vedotin for cycles 3 and 4. The goal of this study is to evaluate the impact of treating non-CR patients (after two cycles of therapy) at an increased dose (from 1.8 mg/kg to 2.4 mg/kg) during cycles 3 and 4. We believe that the 2.4 mg/kg dose will be well tolerated (defined as $\leq 33\%$ of patients with \geq grade 3 non-hematologic toxicity that is assigned an attribution level of at least possibly related to the study drug during cycle 3 or 4) and that treating these patients at the increased dose will increase the CR rate.

With a CR rate of 33.3% -after two cycles of therapy, we expect to achieve 10 patients without CR (in the first 2 cycles) after 15 patients are enrolled (maximum enrollment 20, which has $>90\%$ chance of having 10 patients without CR in first two cycles). With 10 patients treated at the escalated dose of 2.4 mg/kg, with a conversion rate of 25%, the probability of not getting at least one response is less than 6%. If the first 2 cycle response data are pending, accrual will not hold. Accrual will only hold based on stopping due to toxicity, or when 10 patients are treated at the escalated dose of 2.4mg/kg. Patients who are treated with at least one cycle at 2.4 mg/kg will be evaluable at that dose level, even if later dose reduced or discontinued.

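### Section 8.1 uses 60% as both the historical and the target response rate and states no null; its rule succeeds 46% of the time at 60%, so neither 80% power nor 5% error holds there

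*Combined protocol and SAP*

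**What the plan says.** All the design inputs are in section 8.1 (Sample size calculations).

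- Historical rate: "Based on historical data, the assumed ORR in this patient population is 60"%.
- Rate to detect: "The objective of this study is to be able to detect an ORR of at least 60"%.
- Design type: "The study will utilize a Simon two-stage optimal design".
- Stage 1: 23 patients. With 12 or more responders, 14 more are enrolled, for a total of 37.
- Final rule: "The null hypothesis will be rejected if 23 or more of the total sample size of 37 respond".
- Error and power: "This design is based on the use of a two sided test at the 5% level of significance and provides 80% power".

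No value for the null rate appears in section 8.1 or elsewhere in the documents. For the analysis, section 8.1 plans that "exact 95% confidence intervals will be calculated for this estimate" and also says "we will perform descriptive statistical analyses on these data after the study is complete". Section 8.5 repeats the descriptive wording.

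On the state of the trial, section 1.4 reports: "With 30 evaluable patients to date, data from the phase II portion of this study show an ORR of 75"%. Sections 1.4 and 5.5 (new cohort) say that 37 patients have been treated.

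**The concern.** A two-stage single-arm test needs a null rate and a higher alternative rate. Section 8.1 uses the same number for the rate already expected from history and for the rate it wants to detect, so 60% could be either. With no null stated, rejecting the null has no defined meaning, and a reader cannot check the type I error at all.

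The final cut-off also looks too close to 60% for the claimed power. Since 22/37 = 59.5% and 23/37 = 62.2%, 23 is the smallest count with an observed rate of at least 60%. If the true rate is 60%, a cut-off placed there is reached a little less than half the time.

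This rule is the only stated test of the primary endpoint and the only basis given for N = 37. At stake is what may be claimed from the result: a reader could take success to mean that the ORR has been shown to exceed 60%, which the rule cannot support.

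**Working it through.** **Inputs (section 8.1):** n1 = 23, continue if at least 12 respond; n2 = 14, N = 37; reject if at least 23 of 37 respond; ORR 60%; claimed 5% two-sided and 80% power.

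**Formula.** For a true ORR p, with one look at 23 patients and all 37 evaluable:

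P(reject | p) = Σ (x = 12 to 23) Bin(x; 23, p) × P(Bin(14, p) ≥ 23 − x)

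**Attempt to reproduce the plan's figure.** At p = 0.60 the sum is 0.4608. Without the interim look, P(Bin(37, 0.60) ≥ 23) = 0.4645, so the stage 1 rule costs almost nothing. The claimed 80% is not obtained. Read as a type I error, the same 0.4608 stands against a claimed 5%.

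**The written rule over a range of true ORR:**

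| True ORR | P(reject) |
|---|---|
| 40% | 0.5% |
| 45% | 2.6% |
| 50% | 9.3% |
| 60% | 46.1% |
| 65% | 70.4% |
| 70% | 88.4% |

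Solving for p: P(reject) = 2.5% at p = 44.8%, 5% at 47.4%, and 80% at 67.35%. The stated error is therefore met only if the null is 47.4% or less (one-sided 5%) or 44.8% or less (2.5% in the upper tail of a two-sided 5% test). The stated power is met only from about 67.35% upward.

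**Where the shortfall comes from.** The stage 1 gate alone is passed with probability P(Bin(23, 0.60) ≥ 12) = 0.836, which caps power at 60%. With that gate kept, power at 60% by final cut-off is:

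| Final cut-off (of 37) | Power at 60% |
|---|---|
| ≥ 19 | 80.5% |
| ≥ 20 | 76.2% |
| ≥ 23 (written) | 46.1% |

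**Is it an off-by-one slip?** Stage 1 cut-offs of 11 to 13 combined with final cut-offs of 22 to 24 give 33% to 59% at an ORR of 60%. None comes near 80%.

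**A possible source, not proven.** A search of Simon designs shows that the integers 12/23 and 23/37 are the minimax design for 50% versus 70%, one-sided 5%, 80% power. There, 12 and 23 are the largest counts that stop or fail, so the trial continues at ≥ 13/23 and rejects at ≥ 24/37. That version has error 4.8% at 50% and power 80.1% at 70%; the rule as written has 9.3% and 88.4%. The optimal design for the same pair is 8/15 and 26/43. Designs for 40% versus 60% (optimal 7/16, 23/46; minimax 17/34, 20/39) and 60% versus 80% (optimal 7/11, 30/43; minimax 8/13, 25/35) do not give these integers. Neither 50% nor 70% is stated in section 8.1, and even this version has only 32.9% power at 60%.

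**A result on the boundary.** For 23/37 the exact (Clopper-Pearson) 95% interval is 44.8% to 77.5%, ignoring the two-stage sampling. It contains 60%.

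**The case against.** The strongest reply is that little now depends on this. Treatment of the 37 patients is reported, so no accrual decision for this cohort rests on the power. An ORR of 75% in 30 patients means 22 or 23 responders (22/30 = 73.3%, 23/30 = 76.7%). Assume 22, with 7 further evaluable patients and a true ORR of 60%: the chance of at least one more responder, giving ≥ 23, is 1 − 0.4^7 = 99.8%, and the chance of at least two more, giving ≥ 24, is 98.1%. The plan also opens with an aim of estimation, intends an exact interval and calls the analysis descriptive. All of this stands, and it is why no new patients or cut-offs are asked for. It does not make the stated power and error true, and the plan still sets a rejection rule.

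Two technical points also stand as conditions. Section 11.1.2 places an interim analysis after 17 patients, whereas stage 1 has 23. No stopping boundary is attached to the look at 17, so the figures above ignore it, but the two sections need reconciling. The response rate is defined over evaluable patients while the cut-off is counted out of 37; with fewer than 37 evaluable, the probabilities change.

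That the interval for 23/37 contains 60% is a difficulty only if 60% is read as the rate to beat. The 50% versus 70% origin is inference, and the conclusion does not rest on it. Finally, detecting at least 60% names a range, and power does exceed 80% in its upper part; but 60% is the stated minimum, and power there is 46%.

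**Conclusion.** The concern holds. Section 8.1 states no null rate, uses 60% in two roles, and claims error and power that its own rule does not deliver in either role: the rejection probability at 60% is 46.1%, against 80% if 60% is the target and 5% if it is the null. This assumes one decision look at 23 patients and 37 evaluable patients. It needs correcting because it concerns the only stated test of the primary endpoint. The practical effect is on how the result may be described; given the reported interim ORR, the pass or fail outcome itself is unlikely to change.

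**What to change.** 1. Retrieve the original design record and state the null rate, the alternative rate and the sidedness in section 8.1.
2. Keep 12/23 and 23/37 as the governing cut-offs. Patients have been treated and an interim ORR is reported, so changing them now would be post hoc.
3. Replace the sentence on significance level and power with: *Under this rule the exact one-sided probability of rejecting the null hypothesis is 2.6% at a true ORR of 45%, 9.3% at 50%, 46% at 60%, 70% at 65% and 88% at 70%.* Add a note that this assumes 37 evaluable patients and a single decision look at 23, and reconcile that with section 11.1.2.
4. Stop describing 60% as the rate detectable with 80% power. Remove the labels optimal and two-sided unless the record supports them.
5. If the record shows that 50% versus 70% was intended, also report whether the result meets ≥ 13/23 and ≥ 24/37, as a supplement to the written rule.
6. Report the exact 95% interval beside the test result.
7. If no record can be found, say so and present 23/37 as a descriptive threshold instead of a test of an unnamed null.

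The cost is wording and a records search. No patients are added and no cut-off moves, but the stated error and power become less favourable.

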4 SELECTION OF PATIENTS

The total number of patients to be enrolled on this study is 37. Enrollment date is defined as the first day of brentuximab vedotin treatment (i.e., Day 1 of Cycle 1).

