6.4.2 Disease Response Assessments

Responses will be assessed (between Days 15 and 21) as follows as defined in Section 7.1:

- Dedicated CT of chest, neck, abdomen, and pelvis or CT/PET: Cycles 2 and 4
- PET: Cycle 4

In addition, bone marrow aspirate and biopsy are required to confirm responses in patients who have bone marrow involvement at baseline (see Section 7.1). The follow-up bone marrow aspirate and biopsy must be done within 2 weeks of documentation of response. Once the bone marrow is negative no further bone marrow evaluations are required.

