7.1 Response Assessments

Treatment response will be assessed by dedicated spiral CT scan of chest, neck, abdomen, and pelvis and PET scans performed at protocol-specified time points (see Appendix Section 14.1 and Section 6). The determination of antitumor efficacy will be based on objective response assessments made according to the Revised Response Criteria for Malignant Lymphoma (Cheson et al. 2007) and treatment decisions by the investigator will be based on these assessments. Clinical response of progressive disease (PD), stable disease (SD), partial remission (PR), or complete remission (CR) will be determined at each assessment. Selection of up to 6 of the largest dominant nodes or nodal masses to follow for response assessment must be PET FDG-avid at baseline. Investigator evaluation of baseline radiographic assessment will enable study enrollment per Inclusion Criteria based on the presence of measurable disease > 1.5 cm evidenced by CT scan of the neck/chest/abd/pelvis or CT/PET scans. In addition, per the Revised Response Criteria for Malignant Lymphoma, these nodes or masses should be selected according to all of the following: they should be clearly measurable in at least 2 perpendicular dimensions; if possible they should be from disparate regions of the body; and they should include mediastinal and retroperitoneal areas of disease whenever these sites are involved.

If the bone marrow was positive at baseline, a follow-up bone marrow aspirate and biopsy is required and must be negative for assessment of a CR. If the follow-up

morphology is indeterminate, the biopsy tissue must be negative by immunohistochemistry or the patient will be assessed as a PR.

Tumor imaging will be performed at screening, cycle 2, and 4.

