8.4 Populations for Analysis

Hodgkin lymphoma patients refractory to induction chemotherapy or 1st relapsed after induction therapy.

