8.5 Statistical methods

The toxicities observed will be summarized in terms of type (e.g. organ affected or ANC) severity (by NCI CTCAE 4.0 and nadir or maximum values for the laboratory measures), date of onset, duration, reversibility, and attribution. Table will be created to summarize these toxicities and side effects. Baseline information (e.g., the extent of prior therapy) and demographic information will be presented for all patients.

In accordance with the primary study objectives, we will perform descriptive statistical analyses on the data after the study is complete. Response will be assessed by Cheson 2007 criteria and reported as percentage of the evaluable study population. With adequate follow-up time, the secondary endpoints of PFS, overall survival (OS) will be assessed by Kaplan-Meier survival analysis and 95% confidence intervals will be calculated using Greenwood's formula.

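### The primary response rate and its exact confidence interval use an undefined *evaluable* denominator, while the Simon decision rule counts responders among all 37 treated patients

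*Combined protocol and SAP*

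**What the plan says.** Section 8.1 uses two descriptions of who counts. The decision rule enrols 23 patients, adds 14 if at least 12 respond, and ends: "The null hypothesis will be rejected if 23 or more of the total sample size of 37 respond". The analysis paragraph that follows says: "Response rates will be calculated as the percent of evaluable patients that have confirmed CR or PR", and puts the exact 95% interval on that estimate. Section 8.5 repeats the second version: response is "reported as percentage of the evaluable study population".

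Four other places bear on who is in each denominator:

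- Section 4: "Enrollment date is defined as the first day of brentuximab vedotin treatment". Enrolled therefore means treated.
- Section 8.4, on analysis populations, reads in full: "Hodgkin lymphoma patients refractory to induction chemotherapy or 1st relapsed after induction therapy". This describes the disease. It names no treated, intent-to-treat or evaluable set.
- Section 8.2 has the only statement of who is evaluable, and it concerns the new cohort: "Patients who are treated with at least one cycle at 2.4 mg/kg will be evaluable at that dose level". It applies even when the dose is later reduced or treatment stops.
- Sections 6.4.2 and 7.1 set the assessment times: "Responses will be assessed (between Days 15 and 21) as follows" and "Tumor imaging will be performed at screening, cycle 2, and 4".

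**The concern.** The trial's primary endpoint has one denominator for the decision and another, undefined, for the estimate that readers will see. Nothing says how a treated phase II patient without a post-baseline assessment is counted, or whether such a patient is replaced. Those most likely to lack an assessment are patients who die, withdraw or stop early, and few of them will be responders. Dropping non-responders from the denominator leaves the numerator alone, so the rate and both confidence limits can only rise.

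At stake is the published response rate and its interval, not the count decision. The estimate would describe a selected group while the decision describes all treated patients. Close to the cutoff, a trial that misses its rule could report a rate that looks as if it had met it.

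**Working it through.** **1. The rule's denominator.** Section 8.1 gives 23 + 14 = 37 enrolled. By section 4, enrolled means first dose given. Sections 1.4 and 5.5 (new cohort) also refer to 37 treated phase II patients. The cutoff corresponds to 23/37 = 62.2%.

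**2. Can a treated patient lack an assessment?** The first scheduled post-baseline scan is in cycle 2, Days 15–21. With 21-day cycles, cycle 2 starts on Day 22, so the scan falls on Days 22 + 14 to 22 + 20 = Days 36–42. If cycle 2 starts 3 weeks late, as section 5.5 permits, it starts on Day 43 and the scan falls on Days 57–63.

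The end-of-treatment visit (section 6.5) closes only part of this gap. Its response assessment is required only when no radiologic assessment was done in the prior 6 weeks. After a single dose on Day 1, the visit (21 ± 7 days later) falls on Days 15–29. Going back 42 days from Day 29 reaches about Day −13. Read literally, a baseline scan from the last two weeks or so before treatment means that no new scan is triggered. Deaths before the visit are missed as well.

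**3. Effect on the estimate.** The exact (Clopper–Pearson) 95% limits for x responders of n are

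- lower = 2.5% quantile of Beta(x, n − x + 1)
- upper = 97.5% quantile of Beta(x + 1, n − x)

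The number excluded is an assumption, because the documents do not give it. All those excluded are taken to be non-responders. With x = 23, the smallest count that meets the rule:

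| Excluded | x/n | Rate | Exact 95% CI | Change in rate (points) | Change in lower limit (points) |
|---|---|---|---|---|---|
| 0 | 23/37 | 62.2% | 44.8–77.5 | – | – |
| 1 | 23/36 | 63.9% | 46.2–79.2 | +1.7 | +1.5 |
| 2 | 23/35 | 65.7% | 47.8–80.9 | +3.6 | +3.0 |
| 3 | 23/34 | 67.6% | 49.5–82.6 | +5.5 | +4.7 |

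**4. One responder below the cutoff.** With x = 22 the rule is not met.

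| Excluded | x/n | Rate | Exact 95% CI |
|---|---|---|---|
| 0 | 22/37 | 59.5% | 42.1–75.2 |
| 1 | 22/36 | 61.1% | 43.5–76.9 |
| 2 | 22/35 | 62.9% | 44.9–78.5 |

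One exclusion moves the reported rate from below to above the 60% that section 8.1 aims to detect. Two exclusions move it above the 62.2% that the cutoff implies.

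**5. Interim data.** Section 1.4 reports 75% on 30 evaluable patients. 0.75 × 30 = 22.5, which is not a whole number (22/30 = 73.3%, 23/30 = 76.7%). This may be a rounding or reporting slip, and the difference between 30 and 37 may be patients whose assessments were pending. It does not show that anyone was excluded. It does show that evaluable-only reporting is already in use and that a reader cannot tell who is in the denominator.

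**The case against.** The strongest reply is that nothing decisive depends on this. The rule is a count, 23 or more of 37, and it does not change. The estimate is described as descriptive. No passage reports a treated patient without an assessment, so the effect may be zero. Section 1.4 says that all patients but one went on to transplant, and section 5.5 that none of the 37 needed a dose reduction; neither suggests early loss. Early progression can be recorded as a response category, and the end-of-treatment visit includes a response assessment. The one evaluability statement in the plan, in section 8.2, is inclusive. Carried over to the phase II cohort, it would make the two denominators agree. A definition might also stand in an appendix that is not in the text available.

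Much of this is right, and it limits the weight of the point. The decision is unchanged and the size is unknown. But the transplant statement may cover only the 30 evaluable patients, and absence of dose reduction does not rule out discontinuation. The end-of-treatment assessment is conditional, as shown above. No sentence extends the section 8.2 convention to the phase II cohort, and section 8.4, the natural place for a definition, has none. Reading 37 as 37 evaluable patients does not work either, since the rule is written on patients enrolled and has no replacement provision.

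**Conclusion.** The concern holds. The primary rate and its exact interval rest on a denominator that is undefined for the phase II cohort and may be smaller than the 37 that the decision rule uses. Any difference from excluding treated patients without a response can only favour the treatment.

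The size depends on the number excluded. With none there is no effect. With one to three (assumed, all non-responders) and 23 responders, the rate rises by 1.7 to 5.5 points and the lower limit by 1.5 to 4.7 points. The go/no-go count is not affected. The point is worth correcting because it concerns the headline result, has a known direction and costs little to remove.

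**What to change.** In sections 8.1, 8.4 and 8.5:

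- Define the primary response rate as CR plus PR over all phase II patients who received at least one dose, that is, the 37 in the Simon rule.
- Count a patient with no post-baseline response assessment as a non-responder.
- Put the exact 95% interval on that denominator.
- Define *evaluable* for the phase II cohort. Report the evaluable-only rate as a sensitivity analysis, with the number excluded and the reason for each.

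The minimum repair would be to define *evaluable* and say how unassessed patients count. Making all treated patients primary is preferable because it matches the decision rule.

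The cost is text edits in three sections and one extra table row, with no new data. The reported rate may be slightly lower. Interim responses are already known (section 1.4) and 37 patients have been treated (section 5.5), so the amendment must record that the change followed interim data. Relative to the evaluable-only rate, counting unassessed patients as non-responders can only leave the estimate the same or lower it, so the late change cannot flatter the result.

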2.2 Secondary Objectives

The secondary objectives of this study are:

- To characterize the safety, toxicity and tolerability of brentuximab vedotin as a salvage regimen.
- To summarize the stem cell mobilization results of patients receiving brentuximab vedotin as salvage therapy (e.g., total CD34+ cell yield, number of apheresis days, proportion of patients who achieve $\geq 3 \times 10^6$ CD34+ cells/kg)
- To evaluate potential changes in Hodgkin lymphoma biological markers of patients treated with brentuximab vedotin as 1st line salvage therapy.
- To examine and characterize the outcomes of patients who receive brentuximab vedotin as 1st line salvage followed by AHCT (e.g., 2-year PFS/OS/relapse-progression incidence and NRM).

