11.5 Monitoring of Adverse Events and Period of Observation

Adverse events, both serious and non-serious, and deaths that occur during the patient's study participation will be recorded in the source documents. All SAEs should be monitored until they are resolved or are clearly determined to be due to a patient's stable or chronic condition or intercurrent illness(es).

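### PFS counts a death only if lymphoma or acute treatment toxicity caused it, so other relapse-free deaths are in effect censored and 2-year PFS can only be pushed upward

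*Combined protocol and SAP*

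**What the plan says.** Section 2.2 lists the outcomes after transplant as a set: "2-year PFS/OS/relapse-progression incidence and NRM".

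Section 8.1 defines and analyses them:

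- **PFS** runs "until objective or symptomatic relapse or death as a result of lymphoma or acute toxicity of treatment".
- **OS** has no restriction by cause: "OS will be defined as the time from first treatment day (post AHCT) until death".
- **Estimator:** "the endpoints of PFS, overall survival (OS) will be assessed by Kaplan-Meier survival analysis", with Greenwood confidence intervals.
- **Relapse and NRM:** "The cumulative incidence of relapse/progression and non-relapse mortality will be calculated as competing risks".

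Section 8.5 repeats the estimator ("the secondary endpoints of PFS, overall survival (OS) will be assessed by Kaplan-Meier survival analysis") and gives no other definition of PFS. Nowhere do the documents state a censoring rule for PFS, define NRM, give a time window for *acute*, or say whether *treatment* means brentuximab vedotin, the transplant regimen or both. No procedure for judging cause of death is described.

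**The concern.** A reader who sees 2-year PFS will normally assume that every death counts. Under section 8.1 a relapse-free patient who dies of, say, a second cancer, late cardiac disease or an unrelated illness has no PFS event. Such deaths are plausible on the protocol's own account: section 1.1 links multi-agent first-line regimens to secondary malignancies and to cardiac and pulmonary disease, and every patient enrolled has had front-line induction.

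Three things follow.

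- The error runs one way. Leaving out deaths can only raise the estimate.
- The four outcomes may not reconcile. The same death counts in OS, and in NRM on the ordinary meaning of that term, but not in PFS. So 1 − PFS need not equal relapse incidence plus NRM.
- The rule needs a judgement of cause that the plan does not support. Under section 6.1, routine adverse-event collection stops at the later of the end-of-treatment visit and 30 days after the last dose, whereas PFS is followed to 2 years after transplant.

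**Working it through.** The plan states no figure for 2-year PFS, NRM or event counts, so there is nothing to reproduce. The check covers direction, size and whether the fix makes the outcomes reconcile.

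**Inputs.** N = 37 (section 4). Relapses by 2 years, R, and uncounted relapse-free deaths, D, are assumptions. The base case is R = 9 to 11, D = 1 or 2, and complete follow-up to 2 years.

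**Direction.** Kaplan-Meier is a product of factors (1 − d/n) over event times, where d is the number of events and n the number at risk. Recoding a death from event to censoring at the same time removes a factor below 1 and leaves later risk sets unchanged, so the estimate cannot fall. In 20,000 random data sets (5 to 57 patients, with additional censoring) the cause-restricted estimate was never below the all-cause estimate. Carrying such patients forward as event-free to 2 years did not lower it in any scenario tried either.

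**Size, one uncounted death.** All-cause PFS = 1 − (R + 1)/N.

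- If the death is the first event, restricted PFS = 1 − R/(N − 1), and the gap is (R + 1)/N − R/(N − 1), the smallest possible.
- If the death is the last event, restricted PFS = 1 − R/N, and the gap is 1/N, the largest possible.

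For N = 37 and R = 11, the smallest gap is 12/37 − 11/36 = 32.43% − 30.56% = 1.88 points (69.4% reported against 67.6%). The largest is 1/37 = 2.70 points (70.3% against 67.6%).

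For two deaths with R = 11, the smallest gap is 13/37 − 11/35 = 35.14% − 31.43% = 3.71 points and the largest is 2/37 = 5.41 points.

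Enumerating every ordering of the events gives:

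| N | R | D | Min | Mean | Max (points) |
|---|---|---|---|---|---|
| 37 | 9 | 1 | 2.03 | 2.34 | 2.70 |
| 37 | 11 | 1 | 1.88 | 2.24 | 2.70 |
| 36 | 9 | 1 | 2.06 | 2.39 | 2.78 |
| 36 | 11 | 1 | 1.90 | 2.29 | 2.78 |
| 37 | 9 | 2 | 4.02 | 4.66 | 5.41 |
| 37 | 11 | 2 | 3.71 | 4.47 | 5.41 |

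The N = 36 rows assume one of the 37 is not transplanted. Section 1.4 prompts this ("Ultimately all patients, with the exception of one went on to AHCT after additional therapy"), but it reports on 30 evaluable patients to date, so 36 is an assumption.

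**Scale.** With complete follow-up the Greenwood interval has half-width 1.96·√(p(1 − p)/N). For one death at N = 37, p = 27/37 = 0.730 gives 14.3 points and p = 25/37 = 0.676 gives 15.1 points.

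**Do the outcomes reconcile after the fix?** With death from any cause as a PFS event and NRM as death without prior relapse, all-cause Kaplan-Meier PFS was compared with 1 − (cumulative incidence of relapse) − (cumulative incidence of NRM). Over 20,000 simulated data sets (N = 37, exponential event times, censoring uniform over 0.5 to 4 years) the largest difference at 2 years was 7 × 10⁻¹⁶, which is rounding error. The identity holds with censoring too.

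**The case against.** The strongest reply is that section 8.1 openly defines a cause-restricted PFS, so the gap from all-cause PFS is a difference in what is estimated. OS, relapse incidence and NRM are also planned, so the omitted deaths stay visible, and the plan nowhere promises that the four outcomes add up. It is also true that censoring is inferred from the event definition, that bias here means relative to all-cause PFS, and that the mismatch with NRM assumes that term's ordinary meaning. But companion outcomes do not correct the PFS figure that is reported.

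The assumed range of relapses is narrow. Section 1.1 quotes 5-year event-free survival of 65% to 80% in low-risk patients and below 30% in the others, with most relapses within 2 years of transplant. These are background figures, but they allow more relapses. At N = 37 with one uncounted death, 18 relapses give 1.35 to 2.70 points and 22 give 1.05 to 2.70. If the new cohort were pooled (N = 57, which the plan does not specify), 9 to 11 relapses give 1.41 to 1.75. With incomplete follow-up a late death could move the estimate by more than 1/N. These cases widen the illustration and leave the direction unchanged.

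The start date is open to argument, because section 4 ties enrollment to the first brentuximab vedotin dose. The qualifier in the OS and PFS definitions and the wording of section 2.2 still point to the transplant.

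Finally, a lymphoma death with no earlier documented relapse would fall under NRM in the proposed definition. That is an edge case in coding NRM and does not affect all-cause PFS.

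**Conclusion.** The concern holds. As written, the rule drops some relapse-free deaths from PFS, and 2-year PFS can then equal or exceed all-cause PFS but never fall below it. The direction is algebraic and needs no assumption about event rates.

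The size does need assumptions. With 37 patients, complete follow-up and 9 to 11 relapses, it is 1.9 to 2.7 points for one uncounted death (mean 2.2 to 2.3) and 3.7 to 5.4 points for two (mean 4.5 to 4.7). It is zero if no such death occurs before 2 years.

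This is minor. PFS is secondary and descriptive with no test or threshold, the shift is small beside a confidence half-width of 14 to 15 points, OS counts every death, and the primary response rate is untouched. The interval describes sampling error, however, and does not cover a one-directional error in the definition.

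**What to change.** In section 8.1:

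- Define PFS as time from the date of AHCT (stem-cell infusion) to the first of relapse or progression (judged as now) and death from any cause.
- Define OS as time from the same date to death from any cause.
- Define NRM as death without prior relapse or progression, with relapse or progression as the competing event. Add a line on how a lymphoma death without documented relapse is coded.
- Use the same start date and the same transplanted patients for all four outcomes, and one stated censoring rule for PFS, relapse and NRM.

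If the cause-restricted version is still wanted, report it under a different name as a sensitivity analysis, with *acute* and *treatment* defined.

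The cost is a wording change. OS already needs the date of every death, so no new data are required. Section 11.5 gives partial support ("deaths that occur during the patient's study participation will be recorded in the source documents"), though it does not define study participation. PFS no longer depends on a judgement of cause of death. The downside is that reported PFS may be a few points lower than under the current wording.
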